Trial personnel will all be required to participate in a training session before the start of any trial procedures or measurements. Training will include particular attention to core trial elements, such as recruitment, retention, intervention, completeness and quality of data acquisition (e.g., blinding procedures for the data collectors), and data entry. Separately, intervention staff will meet and receive detailed instruction on trial approaches to group and individual behavior change counseling and procedures that ensure data collectors are blinded to treatment assignment. Throughout the trial, periodic re-training/certification sessions will be conducted to ensure all trial-related procedures are being applied in a standard manner. Investigators will also monitor all aspects of study performance to ensure study goal achievement, timeliness and completeness of study visits, completeness and quality of data collection, intervention adherence, and adequacy of the procedures separating data collection from intervention. Study staff and investigators will pay particularly careful attention to the quality of all laboratory measurements, particularly key exposure, outcome, and intervention monitoring variables.

12. Sample Size and Statistical Power

The primary outcome will be the difference in the change of HbA1c between the intervention and usual diet groups from baseline to 6 months of follow-up. Preliminary data from ADEPT suggests that the SD of the 6-month change in HbA1c is 0.28%, with preliminary 6-month follow-up >90%. Based on an estimated standard deviation of change in HbA1c of 0.35% and 95% follow-up, we would need 142 participants to have 80% power to detect a difference in the change in HbA1c from baseline to 6 months of 0.17% between the intervention and usual diet groups. Assuming 95% follow-up, we would need 150 total participants.

In a follow-up analysis of the DPP, a 0.15% decrement in HbA1c at 6 months was associated with a 16% lower risk of incident T2D, adjusting for treatment arm, age, sex, race/ethnicity, household income, and baseline HbA1c.¹¹⁶ In a pooled analysis from the Atherosclerosis Risk in Communities and Framingham Heart Studies, a 0.15% higher HbA1c was associated with an 16% higher risk of T2D over 20 years, a 30% higher risk over 8 years, and a 13% higher risk after 8 years, after adjusting for age, sex, fasting glucose, triglycerides,

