HDL, family history of T2D, SBP, and BMI.¹¹⁷ Additionally, in EPIC-Norfolk, a difference of HbA1c of 0.15% was associated with approximately a 5% higher risk of CHD among those free of CHD, stroke, diabetes, and with HbA1c <7.0%.¹¹⁸

In the DPP study, HbA1c was 0.15% lower among those in the lifestyle intervention arm than in the control arm at 6-months follow-up; HbA1c at study commencement was 5.9% and levels increased in the control arm and decreased in the behavioral intervention arm.²² In a small behavioral intervention study (n=34) of a very low-carbohydrate ketogenic diet compared with a moderate carbohydrate, calorie-restricted, low-fat diet among individuals with type 2 diabetes or prediabetes (HbA1c >6.0%) and elevated body weight (BMI >25), mean HbA1c

decreased from 6.6% to 6.1% in the very low-carbohydrate group and from 6.9% to 6.7% in the moderate carbohydrate group over a 12-month period; additionally, the very low-carbohydrate group had greater reductions in glucose-lowering medications.³⁷

Detectable differences are listed for HbA1c and secondary outcomes in **Table 5**, based on data from prior studies.^{30,53,56,119} These were calculated for unpaired t-tests, power of 80%, two-sided alpha of 0.05, and assuming 95% follow-up of 150 participants, which would yield an estimated 142 participants.

Table 5. Minimum detectable differences

Change from baseline to 6 months in	SD	Detectable Difference
HbA1c, %	0.35	0.17
Fasting glucose, mg/dL	12.5	5.9
Fasting insulin, mU/mL	7.0	3.3
HOMA-IR	2.0	0.95
SBP (mmHg)	4.2	2.0
DBP (mmHg)	3.0	1.4
Total/HDL ratio	1.2	0.57
Body weight (kg)	6.6	3.1
Waist circumference (cm)	8.0	3.8
Estimated CVD risk (%) [*]	6.7	3.4

*10-y CVD risk, among estimated 85% or 126 participants free of CVD

13. Data Management and Analysis

13.A. Data management

Personnel will double-enter all study data. Prior to entering data, the study coordinator will conduct quality control on all study forms, study measures, and laboratory data. Data will be cleaned and logically checked.

13.B. Data analysis plan

The data will be analyzed using *intention to treat*; this involves comparing the primary and secondary outcomes between participants based on randomization assignment.

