13.B.1. Exploratory data analysis: We will express group data for variables with a normal distribution as mean \pm standard deviation and for variables not normally distributed as median and interquartile ranges (or will log-transform the variables to obtain a normal distribution). We will compare means and percentages of baseline variables across the intervention and usual diet group to assess similarity of these groups at randomization.

13.B.2. Primary, secondary, and exploratory outcomes: We will test the primary study hypothesis that there is a greater reduction in HbA1c from baseline to 6 months in the intervention group than in the usual diet group. To do this, we will use linear regression with change in HbA1c from baseline to 6 months as the dependent variable

We will use Bland-Altman plots to explore whether there is a systematic difference in HbA1c measured by LabCorp compared with DDL. If there is not a systematic difference in HbA1c measured at these two laboratories, to improve precision in the estimate of the primary outcome (difference in change in HbA1c between the intervention and control groups), we will use the weighted average of change in HbA1c measures from the two labs as the outcome (weights defined as the ratio of the variance for each lab over the sum of the variance) (50). If we observe a systematic difference between HbA1c measured at LabCorp and DDL, we will use HbA1c measured at DDL.

We will use a similar approach to test the difference in the change between baseline and 6-month values of secondary outcomes (Specific Aim 2) and exploratory outcomes. In exploratory analyses, we will also test the difference in the change between baseline and 3-month values of outcomes (HbA1c, fasting glucose, systolic blood pressure, total-to-HDL cholesterol, body weight, insulin, HOMA-IR, diastolic blood pressure, waist circumference, and estimated CVD risk). We will also explore the use of mixed effects models to assess overall net change in HbA1c (by treating time as a linear variable) and other outcomes over the full study period. For each outcome, we will test modeling assumptions and will consider transformation of outcomes, if needed, to meet modeling assumptions. We will also perform sensitivity analyses using Markov-chain Monte Carlo techniques to impute missing values of the outcomes, using covariates for this imputation and will compare results from this analysis with our primary findings.

15. Anticipated Challenges

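### The primary HbA1c estimate omits randomized participants without a 6-month value and makes no use of their 3-month HbA1c, so it is open to bias if dropout follows early response

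*Combined protocol and SAP*

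**What the plan says.** All of this is in the combined protocol and SAP.

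- **Analysis principle (Section 13.B).** The data are to be analyzed by intention to treat, explained as follows: "this involves comparing the primary and secondary outcomes between participants based on randomization assignment". Nothing is said there about participants without an outcome.
- **Primary model (Section 13.B.2).** "we will use linear regression with change in HbA1c from baseline to 6 months as the dependent variable". The secondary outcomes are handled in a similar way.
- **Missing outcomes (Section 13.B.2).** The investigators will "perform sensitivity analyses using Markov-chain Monte Carlo techniques to impute missing values of the outcomes" and set the results beside the primary findings. The imputation uses covariates that are not listed.
- **3-month HbA1c.** Section 10.B.5 has HbA1c measured at the 3-month visit by both laboratories. In Section 13.B.2 these values appear in two places, both exploratory: a test of change to 3 months, and mixed models that treat time as linear and address net change over the whole study.
- **Sample size (Section 12).** The calculation is "Based on an estimated standard deviation of change in HbA1c of 0.35% and 95% follow-up". Table 5 rests on 150 randomized, "which would yield an estimated 142 participants". Early experience in the trial is given as "with preliminary 6-month follow-up >90" percent, not split by arm.

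**The concern.** The primary regression can include only people who have a 6-month HbA1c, and no rule brings the others into the primary estimate. The sizing agrees with this reading, because it counts 142 of 150 as analyzed.

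This matters if the people who are lost differ from those who stay, and differ by arm. That is plausible here. Participants know their assignment (Section 7.C). The diet arm has 11 in-person sessions and 7 telephone follow-ups (Section 8.A), while attendance at the control arm's monthly sessions is optional (Section 8.B). Participants are told their weight during the trial (Section 10.A.2), so a diet-arm participant may know of a poor response before month 6. Section 15 itself lists adherence and follow-up as main challenges.

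If poor early responders in the diet arm leave more often, those who remain look better than the arm as randomized, and the benefit is overstated. Part of the information that would correct this, the 3-month HbA1c, is already collected.

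**Working it through.** **1. Inputs from the documents.** 75 per arm; SD of change 0.35; difference 0.17; follow-up 95%; two-sided alpha 0.05; power 80%; unpaired t-test (Section 12: "These were calculated for unpaired t-tests, power of 80%, two-sided alpha of 0.05, and assuming 95% follow-up of 150 participants").

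**2. The plan's own figure.** 142/0.95 = 149.5, so 150 randomized and 71 per arm analyzed. The detectable difference by t-test is 0.166, which rounds to the stated 0.17. Power at exactly 0.17 is 82.0%. At 90% follow-up (135 analyzed, 67.5 per arm) it is 80.0%. Lost power is therefore a minor matter; the issue is bias.

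**3. General size of the bias.** If a share m of one arm is missing and the missing have a mean change worse by g than the observed, the observed mean of that arm is too favorable by m × g. I assume g between 0.17 and 0.35, in the diet arm only:

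- m = 5%: 0.05 × 0.17 = 0.009 to 0.05 × 0.35 = 0.018
- m = 10%: 0.10 × 0.17 = 0.017 to 0.10 × 0.35 = 0.035

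**4. Linking g to early response.** The following are assumptions, not document figures: 3- and 6-month changes are normal with SD 0.35 and correlation ρ of 0.5 to 0.7, the true difference is -0.17, and the chance of dropout rises by a factor of e per SD of worse 3-month change. Dropouts then average one SD worse at 3 months and ρ × 0.35 worse than their whole arm at 6 months. The observed mean is too favorable by [m/(1 - m)] × ρ × 0.35:

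- m = 5%: (0.05/0.95) × 0.175 = 0.009 for ρ = 0.5; (0.05/0.95) × 0.245 = 0.013 for ρ = 0.7
- m = 10%: (0.10/0.90) × 0.175 = 0.019; (0.10/0.90) × 0.245 = 0.027

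**5. Simulation.** 75 per arm, at least 4,000 replicates per setting, control arm 5% missing. Exaggeration of the benefit by the observed-case analysis:

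| Missing, diet vs control | Selective in diet arm only | Selective in both arms |
|---|---|---|
| 5% vs 5% | 0.009 to 0.013 | 0 |
| 10% vs 5% | 0.015 to 0.026 | 0.008 to 0.011 |
| 15% vs 5% | 0.025 to 0.038 | 0.016 to 0.022 |

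One simulated value in the first row was 0.0136. Its Monte Carlo error is 0.0587/√4000 = 0.0009, so it agrees with the 0.013 in step 4. At higher missingness the simulation falls slightly below the formula, because a dropout probability cannot exceed 1. A weaker link between response and dropout gives less: at ρ = 0.7, about 0.005 for 10% vs 5% and 0.011 for 15% vs 5%.

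**6. Scale.** Against the 0.17 target, 0.005 to 0.026 is 3% to 15%, and 0.011 to 0.038 is 6% to 22%. The standard error with 71 per arm is 0.35 × √(2/71) = 0.059, so a bias of 0.026 is 0.026/0.059 = 0.44 standard errors and 0.005 is under 0.1. The 10% vs 5% split averages 7.5% missing, within the follow-up seen so far. The 15% vs 5% split averages 10%, at its edge.

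**7. What the 3-month value recovers.** When every dropout has a 3-month HbA1c, a likelihood-type estimate that uses it had bias of at most 0.002 in all settings. When half of the dropouts lack it (15% vs 5%, selective in both arms), the observed-case estimate was -0.191 and the 3-month-based estimate -0.179, against a truth of -0.170. The bias falls from 0.021 to 0.009, so a little under half remains.

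**8. Precision.** With missingness completely at random, both analyses are unbiased. Using the 3-month value lowered the standard error from 0.0591 to 0.0588 at the least (0.5%) and from 0.0608 to 0.0590 at the most (3%).

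**The case against.** A reader might infer that the plan breaks its own intention-to-treat commitment. The documents do not support that. Section 13.B explains the term as comparison by assigned arm, an observed-case regression by assigned arm meets that, and the expected 142 of 150 is stated openly.

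The plan is also not silent on missing data. It has an imputation analysis, and nothing excludes 3-month HbA1c from its covariates. The exploratory mixed models can include participants who have only a 3-month value. Losses are actively limited: Section 7.B commits to every effort at complete follow-up, Section 10.A.2 allows a local laboratory draw for participants who move, and Section 8.D pays for visits.

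The size is modest and depends on assumptions. The dropout mechanism, its strength and the correlation are not in the documents. If missingness is unrelated to response, or equal at 5% with the same mechanism in both arms, there is no bias. Nothing in the documents shows that the 3-month value is the best predictor of the 6-month value or of who leaves.

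Finally, the sentence that states the primary model ends without a full stop in the text available, so a list of covariates may have been lost.

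Most of this stands as a limit on severity, but none of it repairs the primary estimate. Imputation is explicitly a sensitivity analysis. The mixed models are exploratory and, with linear time, target net change rather than the 6-month contrast. Baseline covariates would not bring back a participant who has no outcome.

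**Conclusion.** The concern holds as a weakness in the choice of primary analysis, not as a contradiction. The primary estimate rests on participants with a 6-month HbA1c and leaves a relevant, already collected measurement to exploratory work. If dropout in the diet arm follows early response, the estimate favors the diet.

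For a true difference of -0.17 the exaggeration is 0 to about 0.013 with 5% missing in each arm, 0.005 to 0.026 at 10% versus 5%, and 0.011 to 0.038 at 15% versus 5%. These ranges rest on an assumed correlation of 0.5 to 0.7 and on dropout chances that rise by up to a factor of e per SD of worse 3-month response. No single figure within them should be relied on.

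Two stronger readings should be resisted. One is that a better model would gain useful precision; the gain is 3% at most. The other is that it would remove the bias altogether. It does so only where missingness depends on data actually collected. The strictest carbohydrate target applies throughout the first 3 months, so some losses may come before the 3-month visit.

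The change is worth making because it costs little and settles the choice of method before results are seen.

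**What to change.** In Section 13.B.2, make the primary analysis a likelihood-based repeated-measures model with baseline, 3-month and 6-month HbA1c, categorical time, an arm-by-time term and all randomized participants. State that the 6-month arm contrast is the primary estimate. Multiple imputation that includes arm and 3-month HbA1c is an acceptable alternative as primary. Keep the observed-case regression as a sensitivity analysis. Name arm and 3-month HbA1c in any imputation model. Apply the same rule to the secondary outcomes, and state that the rule for combining the two laboratories applies at 3 months as well as at 6.

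The cost is SAP wording and slightly more modeling, with no new data collection. The model assumes that values are missing at random given the observed data, and it cannot correct for participants who leave before the 3-month visit. Missing values should therefore be reported by arm and by last visit attended, and a sensitivity analysis that departs from missing at random would be a sensible addition.
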